### **6.3. 24/7 Access for Urgent Protocol-Related Medical Issues/Questions**

In a study-related health emergency, when the study Medical Monitor(s) cannot be reached by a caller, an on-call physician can be reached 24 hours per day/7 days per week for discussion of urgent protocol medical-related questions. The on-call physician can be reached as follows:

- Telephone: [REDACTED] (global reachable number) (telephone number allowing a global reach from both landlines and mobile phones – NOT a toll-free number).
- [REDACTED] - This internet page contains a list of country-specific contact numbers. Countries not listed here need to dial the global reachable number as indicated above. There may be restrictions when dialing a country-specific number from a mobile phone.

## 7. STUDY CONDUCT AND VISIT SCHEDULE

### 7.1. Study Visits

Details of assessments at each visit are presented in the [Schedule of Assessments](#).

#### 7.1.1. Screening

##### 7.1.1.1. Initial Screening

Screening procedures will occur after the subject signs and dates an Institutional Review Board (IRB) or Ethics Committee (EC) approved informed consent form (ICF) and provides authorization to use protected health information (See Section 12.1.3). The ICF will be completed prior to conduct of any study-specific procedures.

Screening procedures will be conducted as listed in the [Schedule of Assessments](#). Screening will occur over a ten-week period. All Screening assessments must occur no earlier than 70 days before the first dose of study drug at the Day 1 visit unless otherwise approved by the study Medical Monitor. Screening assessments should be performed and confirmed sequentially as follows: a) medical history and other non-invasive assessments, b) laboratory assessments, c) MRI-PDFP and MRE and, lastly, d) liver biopsy.

Histological evidence of definite NASH based on the judgement of the central histopathologist is required for study entry. Tissue samples from a previous biopsy taken within 26 weeks of the Screening visit may be used or a biopsy may be performed during the Screening window. Refer to Section 8.4.8 and the study binder for detailed instructions. If a new liver biopsy is required to satisfy entry criteria, subjects must satisfy all other study entry criteria before the liver biopsy is performed.

Slight extensions to the Screening window for such cases as delayed biopsy or imaging results, or for logistical reasons, may be permitted only with the approval of the Medical Monitor. In such cases, the Medical Monitor will determine if any Screening assessments, e.g., safety labs, may need to be repeated.

##### 7.1.1.2. Retest/Rescreen and Screen Failures

After all Screening assessments are completed, subjects who satisfy all entry criteria (i.e., meet all inclusion criteria but none of the exclusion criteria) should be enrolled into the study.

**Retest:** Subjects with an out-of-range lab value or multiple out of range values, not consistent with the subject's medical history or that may reflect erroneous results based on PI judgement, may retest the respective lab(s). A retest and all remaining assessments must occur within the 8-week Screening window.

**Rescreening:** Subjects who did not qualify for study entry and are, or will be, out of the 10-week Screening window may be rescreened once under the following circumstances with the approval of the Medical Monitor. In each case, the Medical Monitor will determine which, if any, of the Screening assessments may not need to be repeated.

- Subjects who have abnormal laboratory results, which may potentially reflect erroneous results, based on PI judgement, and have exceeded the allowable Screening window for retesting of these parameters
- Subjects who have recently initiated concomitant medications requiring a stable regimen or requiring a medically necessary dose modification, or who have recently discontinued medications and have not yet met the wash out period, but otherwise met all study criteria performed, may rescreen once these respective requirements are met per protocol
- Subjects who are eligible based on completion of all Screening assessments but transiently (for personal reasons) unable to commit to all upcoming study visits and procedures
- Subjects who were impacted by COVID-19 restrictions may rescreen provided the assessments conducted to date meet eligibility and/or retesting criteria.

**Screen Failures:** Subjects who do not satisfy all entry requirements (i.e., meet all inclusion criteria and do not have any of the exclusion criteria) either following Screening or, if appropriate, following retest or rescreen will be considered screen failures.

### 7.1.2. Baseline (Day 1)

Subjects who meet all inclusion criteria and none of the exclusion criteria will report to the clinic on the morning of Study Day 1 after fasting overnight for a minimum of 8 hours. Site personnel will conduct a thorough review of applicable inclusion and exclusion criteria to ensure the subject satisfies all eligibility criteria; subjects who continue to satisfy eligibility requirements will be randomized in a 1:1:1 ratio to their treatment group. Predose assessments and procedures will be conducted as noted in the [Schedule of Assessments](#) and considered Baseline values.

After predose study procedures are completed including predose blood collection for PK and biomarker analysis, subjects will receive the first dose of study drug in the clinic. Postdose blood samples for PK and biomarker analysis will be collected as described in Section 8.4 and shown in the [Schedule of Assessments](#).

Before leaving the clinic, subjects will receive study drug and instructions on how to take the drug at home. Subjects will also be given the two pruritus measurement scales (Section 8.3.5) with instruction on how to complete the scales at home.

### 7.1.3. Treatment Period Visits (Day 7 through Week 72/EOT)

**Phone Contact:** On Day 7, sites will contact subjects by phone to assess AEs, inquire about concomitant medications taken during the past week, and confirm subjects are taking study drug appropriately. Site personnel will also remind subjects to complete the pruritus visual analog and 5D-itch scales and to bring the scales back with them to the next clinic visit.

At Weeks 52, 60 and 68, the site will contact the subject by phone to assess drug accountability, concomitant medications, and AE/SAEs. In addition, for females of child-bearing potential, the site will confirm that the at-home pregnancy test was performed and that the results were negative. If the results were positive, the procedures listed in Section 8.4.6 should be followed.

**Clinic Visits:** All subjects will be requested to return to the clinic for on-treatment study visits as follows: Weeks 2, 4, 8, 12, 16, 20, 24, 28, 32, 36, 40, 44, 48, 56, 64, and 72 following the Day 1 (initial dosing) visit. Note that all treatment visit weeks are determined based on day of initial

dosing. Subjects will be instructed to fast overnight for a minimum of 8 hours prior to each visit so that safety laboratory samples can be drawn fasted. Treatment period assessments per visit are shown in the [Schedule of Assessments](#).

Refer to Section 5.7 for instructions on study drug dosing. Refer to Section 8.4 for instructions on collection of safety laboratory samples.

At the end of the treatment period, subjects will complete the EOT visit. Subjects who complete the full scheduled 72 weeks of treatment will complete the EOT assessments at the Week 72 visit. Subjects who discontinue treatment early should complete EOT assessments at the time of treatment discontinuation (if in the clinic) or within one week following last dose of study drug if the subject discontinues treatment while not in the clinic. Procedures performed are specified in the [Schedule of Assessments](#).

Subjects should take their last dose of study drug in the clinic at the Week 72 visit.

#### **7.1.4. Safety Follow-up Period (End of Study Visit)**

All subjects, including those who discontinue treatment early, should return to the clinic for the EOS visit 4 weeks after the last dose of study drug for follow-up safety assessments ([Schedule of Assessments](#)). For subjects who complete the study, the EOS visit will be scheduled during Week 76.

Any subject with ongoing AEs/SAEs at the EOS visit should be followed until resolution of their AE/SAE or until the PI has determined that the event has stabilized as discussed in Section 9.3.

## **7.2. Subject Withdrawal / Early Termination**

Subjects may withdraw from the study at any time at their own request, or subjects may be withdrawn at any time at the discretion of the PI or Enanta for safety, behavioral, or administrative reasons. However, the PI should consult with the Sponsor's Medical Monitor where possible before prematurely removing a subject. For any subject who decides to withdraw from the study, the PI should inquire about the reason for withdrawal, request that the subject to return all unused investigational product(s), request that the subject return for a final visit, if applicable, and follow-up with the subject regarding any unresolved adverse events. Although a subject may discontinue study treatment, every effort must be made to continue the subject on the study, returning for the EOT visit (if prematurely discontinuing treatment) and the safety follow-up visit.

If a subject withdraws from the study and also withdraws consent for disclosure of future information, no further evaluations should be performed and no additional data should be collected. Enanta may retain and continue to use any data collected before such withdrawal of consent.

For safety monitoring purposes, subjects who withdraw after receiving study drug should return to the clinic within one week and undergo the EOT evaluations ([Schedule of Assessments](#)). Subjects should then return for the Safety Follow Up assessments (EOS visit) 4 weeks after the last dose of study drug. Any subject who withdraws with ongoing AEs/SAEs should be followed until resolution of their AE(s) or until the PI has determined that the AE(s) has stabilized.

Site personnel will attempt to contact any subject who does not return to the clinic for scheduled visit at least three times using the subject's preferred method of communication, followed by a certified letter if the three attempts were unsuccessful. Any subject who still cannot be reached following those attempts will be considered Lost to Follow-up. These subjects will be included in the analysis as indicated in Section 11.

### **7.2.1. Withdrawal Criteria**

Subjects may be discontinued from the study at any time if the subject, PI or Sponsor determines that it is not in the best interest of the subject to continue participation. Reasons for discontinuation include:

- Adverse Event
- Lack of efficacy
- Lost to follow-up
- Withdrawal by subject
- Protocol deviation (including non-compliance with study drug dosing or study procedures)
- Pregnancy
- Sponsor's decision to terminate the study
- Other

Subject-specific stopping rules due to AEs and/or laboratory abnormalities are outlined in Section 10.1.

Subjects who prematurely withdraw from the study for any reason after having been randomized will not be replaced.

### **7.2.2. Documentation of Withdrawal of Subjects**

The reason for early withdrawal/termination/lost-to-follow-up of any subject from the study must be documented on the appropriate eCRF. If the reason for early withdrawal is an AE or an abnormal laboratory value, the specific event or test result, if available, should be recorded on the AE eCRF and the subject should be monitored until the event is resolved or deemed stable by the PI.

## **7.3. Site or Study Discontinuation**

### **7.3.1. Study Discontinuation**

The Sponsor has the right to terminate this study at any time. Reasons for terminating the study may include, but are not limited to, the following:

- The incidence or severity of AEs in this or other studies indicates a potential health hazard to subjects.
- Subject enrollment is unsatisfactory.
- A decision from the IRB/EC or regulatory authority to terminate the study.

If the study is suspended or terminated for safety reasons, Enanta will promptly notify the PI and will also inform the regulatory authorities of the suspension or termination of the study and the

reasons for the action. The PI is responsible for promptly informing the IRB/EC and providing the reasons for the suspension or termination of the study.

### **7.3.2. Site Termination**

A single site may warrant termination under the following conditions:

- Failure of the site to enroll subjects into the study at an acceptable rate
- Failure of the site to comply with pertinent governmental regulations as appropriate
- Submission of knowingly false information from the research facility to the Sponsor, clinical monitor, or governmental authority
- Failure to adhere to the protocol requirements
- Data recording is inaccurate or incomplete
- PI does not adhere to the protocol or applicable regulatory guidelines in conducting the study

### **7.3.3. Study Termination Procedures**

If the study is terminated by Enanta for one of the reasons listed above, or upon completion of the study, the following activities must be conducted by the study monitor and/or site personnel:

- Return of all study data to Enanta or designee
- Respond to and complete all requests for data clarifications
- Accountability and final disposition of used and unused study drug
- Review of site records for completeness
- Shipment of all applicable biological samples (including PK samples) to the designated laboratory

## **8. STUDY PROCEDURES/EVALUATIONS**

### **8.1. Timing of Assessments**

The timing of assessments is shown in [Schedule of Assessments](#).

### **8.2. Demographics and Medical History**

Demographics and baseline characteristics including date of birth, gender, race, ethnicity and medical history will be obtained from each subject and entered in the eCRF as reported. As a general rule, all medical events occurring within the last 6 months should be recorded. For events which occurred more than 6 months ago (and which are not ongoing), only significant or relevant events should be entered on the eCRF. Any items in the history that are still ongoing should be noted as such in the eCRF. All surgeries occurring in adulthood should be recorded in the eCRF. Whenever possible, the date of diagnosis of NASH should be recorded.

### **8.3. Clinical Evaluations**

#### **8.3.1. Vital Sign Measurements, Body Temperature and Electrocardiograms**

Vital signs will include heart rate (HR), respiratory rate, and blood pressure (BP). Vital signs will be measured at times shown in the [Schedule of Assessments](#) after the subject has been supine for 5 minutes and before dosing.

Body temperature should be taken at the Screening, Day 1, and EOS visits according to site standard practices.

Resting 12-lead ECGs will be performed locally and recorded at the times indicated in the [Schedule of Assessments](#) after the subject has been supine for 5 minutes and before dosing. A standard bedside 12-lead ECG machine that calculates HR and measures the PR, QRS, QT, RR, and QTc (QTcF) intervals should be utilized. If the site does not have an ECG machine that calculates these values, the site will need to calculate the values. If a blood draw and ECG are scheduled at the same time, then the ECG should be obtained first.

The normal ranges for the ECG are as follows:

- PR: 120 - 220 msec
- QRS: 70 – 120 msec
- QT:  $\leq$  500 msec
- QTcF:  $\leq$  450 msec
- Heart Rate: 50 – 100 bpm

The PI or designee should review the ECGs in real-time for gross abnormalities and interval measurements of concern (absolute readings and for postdose ECGs, change from baseline). Ranges outside of the normal ranges listed above should be recorded as abnormal. The clinical interpretation by the PI or designee of the ECGs should be recorded on a hard copy of the ECGs (i.e., normal, abnormal clinically significant [CS] or abnormal nonclinically significant [NCS]).

The PI or designee must repeat any ECG where the QTcF interval  $>450$  msec, or absolute QT  $>500$  msec, or with a change from Baseline in QTcF  $>60$  msec. These abnormal ECGs must be repeated once regardless of whether or not the values are considered clinically significant by the PI or designee. Also, ECGs may be repeated at the discretion of the PI to account for erroneous readings.

Prior to dosing, the Baseline ECG must be reviewed to confirm that no clinically significant cardiac abnormalities are present.

### **8.3.2. Physical Examination**

The PI or designee will perform the physical examination. A full physical examination will be conducted at Screening, Week 12 and EOS as indicated in the [Schedule of Assessments](#) and will include a review of the following systems: head/neck/thyroid; eyes/ears/nose/throat (EENT); respiratory; cardiovascular; chest, lymph nodes; abdomen; skin; musculoskeletal; and neurological. Breast, anorectal, and genital examinations will be performed when medically indicated. All subsequent physical examinations will be targeted to new signs and symptoms including specific assessments of any changes from previous status. Only clinically significant abnormalities should be recorded in the eCRF (e.g., use of contact lenses does not need to be recorded).

### **8.3.3. Weight and Body Mass Index (BMI)**

Height and body weight should be obtained with the subject in light clothes and no shoes. Body mass index should be calculated at Screening (to assess eligibility) according to the following equation:

$$\text{BMI} = \text{weight (kg)} / \text{height (m)}^2$$

These measurements will be obtained as specified in the [Schedule of Assessments](#).

### **8.3.4. Quality of Life Assessment**

Quality of life will be assessed using standardized, validated questionnaires including SF-36 and CLDQ-NASH. In addition, Dermatology Life Quality Index (DLQI) will be completed by subjects who report pruritus. Instructions on administration of the questionnaires by the site and completion of the questionnaires by the subject will be provided in the study binder.

### **8.3.5. Assessment of Pruritus**

Pruritus will be monitored in this study at the times indicated in the [Schedule of Assessments](#). As listed below, two separate scales may be used to assess pruritus in subjects:

- First, an itch visual analog scale (VAS) will be used to record the intensity of the event ([Furie et al., 2013](#)). Site personnel should instruct the subject to draw a line on the scale corresponding to the maximum intensity of itch within the last two weeks.
- If VAS score is greater than zero (i.e. itch), a multidimensional 5D-itch scale developed by Elman ([Elman et al., 2010](#)) will be used to assess five different dimensions of pruritus within the last two weeks. The five dimensions assessed are duration, degree, direction, disability, and distribution.
- The scales should be administered as indicated in the study binder.

The scales will be completed by the subject in the clinic during the visit for the in-clinic visits as indicated in the [Schedule of Assessments](#). For the Day 7 phone contact, the subject will be given a copy of the scales on Day 1 to take home so that he/she can record pruritus on Day 7 ( $\pm 1$  day), preferably immediately preceding or during the phone contact with the site.

In addition, **if a subject experiences pruritus** between clinic visits the subject should contact the site as soon as possible:

- to discuss the event,
- to obtain guidance on how to manage the side effect(s),
- and to get specific instructions on how to complete the VAS, 5D-itch and additional evaluations through resolution of the event.

Additional details relative to management of subjects who experience pruritus are included in a separate study binder.

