### 8.6.3 Analysis of secondary efficacy endpoint(s)

All analysis of secondary efficacy endpoints will be performed on the ITT population. Secondary endpoint related to PK data will be analyzed using subjects in the PK population. Secondary endpoints will be analyzed for treatment group differences.

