#### **8.6.3.2.1 Change from baseline in 5D-itch scale and Visual Analog Score (VAS) through week 72**

Pruritus will be monitored in this study at day 1, 7, weeks 2, 4, 8, 12, 16, 20, 24, 28, 32, 36, 40, 44, 48, 56, 64, 72 and EOS.

Observed values, change from baseline, and percentage change from baseline for VAS scores and each dimension of 5D-itch scale and overall score will be summarized using an 8-number summary by visit and treatment group.

Change from baseline for VAS and 5D-itch scale will be analyzed using a restricted maximum likelihood-based mixed model repeated measures (MMRM) technique. The model will include treatment, visit, treatment-by-visit interaction as fixed effects along with baseline NAS score and baseline score for VAS and 5D-itch scale as covariate respectively. Variance-covariance structure to be used to model the within-patient error and results to be presented are described in [Section 8.6.1](#). The details for calculation of score is given in [Appendix B](#).

A by-subject listing will be provided for observed and derived variables for VAS and 5D-itch scale.

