## Appendix B – Scoring for Scales

### 5D-itch scale

5D-itch scale is developed by Elman (Elman, Hynan, Gabriel, & Mayo, 2010) and will be used to assess pruritus in subjects. The five dimensions (aka domains) assessed in 5D-itch scale are duration, degree, direction, disability, and distribution.

The disability domain will be the highest score obtained from the daily activities of sleep, leisure/social activities, housework/errands, and work/school. The disability domain will only be calculated if at least 3 daily activities are documented.

The distribution domain includes 16 locations of itch and is categorized to a scale of 0 to 5, based on the sum of the number of affected locations: sum of 0 to 2 = score of 1, sum of 3 to 5 = score of 2, sum of 6 to 10 = score of 3, sum of 11 to 13 = score of 4, sum of 14 to 16 = score of 5.

The total 5D score is obtained by summing up the five domain scores and ranges between 5 (no pruritus) and 25 (most severe pruritus). The total score will not be calculated if any of the domain scores is missing.

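### If sites give the 5D-itch only when VAS is above zero, subjects without itch on Day 1 have no 5D change score, and the visible SAP text has no rule that gives them one

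*Protocol*

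**What the plan says.** **Administration.** Protocol 8.3.5 puts the VAS first and then sets a condition for the second scale: "If VAS score is greater than zero (i.e. itch), a multidimensional 5D-itch scale". Both scales look back over two weeks. The same section defers to the study binder for how the scales are given. Protocol 7.1.2 has subjects leave the Day 1 visit with both scales, and 7.1.3 has sites remind subjects to complete both for Day 7, with no condition stated. Footnote 15 of the Schedule of Assessments, repeated in SAP Table 1, covers every subject whether or not they itch, but speaks of at most two scales and points back to 8.3.5.

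**Analysis.** Change from baseline in 5D-itch and VAS is a named secondary endpoint (Protocol 2.2.2, SAP 4.2). SAP 8.6.3 sets the population: "All analysis of secondary efficacy endpoints will be performed on the ITT population". SAP 8.6.3.2.1 summarises "Observed values, change from baseline, and percentage change from baseline for VAS scores and each dimension of 5D-itch scale and overall score" by visit and arm, and adds a model: "Change from baseline for VAS and 5D-itch scale will be analyzed using a restricted maximum likelihood-based mixed model repeated measures (MMRM) technique". Its covariates are "baseline NAS score and baseline score for VAS and 5D-itch scale as covariate respectively". SAP Table 2 takes baseline as the last non-missing value before first dose, and change as the post-baseline value minus baseline.

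**Scoring.** SAP Appendix B says that the 5D total "ranges between 5 (no pruritus) and 25 (most severe pruritus", and on incomplete forms: "The total score will not be calculated if any of the domain scores is missing". For the distribution domain the lowest category is "sum of 0 to 2 = score of 1".

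**The concern.** On the conditional reading, whether a 5D score exists depends on the quantity that the scale measures. A subject who does not itch before dosing gives no baseline 5D and so can never have a 5D change, however severe the itch that later starts on drug. A subject who itches on Day 1 and then stops has no 5D at the visits where VAS is 0, so full resolution is also missing.

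The effect of EDP-305 on pruritus is a stated secondary objective, and the protocol calls pruritus the most frequent treatment-emergent event with the drug at 2.5 mg. If the condition was applied, the 5D change analysis would describe only subjects who already itched at entry, and only while they itched. It could not show itch that begins on treatment in anyone else.

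**Working it through.** The plan gives no figure to reproduce here. The check is a trace through the rules, followed by an illustration of size.

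**Trace: a subject with VAS = 0 on Day 1, if 8.3.5 is followed**

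1. The 5D is not given on Day 1 (Protocol 8.3.5).
2. The pruritus scales start on Day 1 and are not scheduled at Screening (Schedule of Assessments, SAP 8.6.3.2.1). No earlier value can serve as baseline.
3. With no domain scores, Appendix B produces no total.
4. Change = post-baseline − baseline, so it is missing at every visit. Percentage change is missing too.
5. The mixed model needs both the change and the baseline 5D covariate, so the subject contributes no record. The note under the sample code in SAP Appendix A calls for data without imputation.

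**What is lost for one subject**

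Five domains at a minimum of 1 give 5 × 1 = 5, which matches the no-pruritus end of the range in Appendix B.

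| Case | Change if VAS = 0 is scored 5 | As written |
|---|---|---|
| Day 1 VAS = 0, later 5D total 10 | 10 − 5 = +5 | missing |
| Day 1 VAS = 0, later 5D total 15 | 15 − 5 = +10 | missing |
| Day 1 VAS = 0, later 5D total 20 | 20 − 5 = +15 | missing |
| Day 1 5D total 10, later VAS = 0 | 5 − 10 = −5 | missing |

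The first three rows and the last differ in kind. Leaving out subjects by Day 1 VAS selects on a pre-dose variable: it narrows the population but keeps the comparison randomised within it. Losing visits where VAS has fallen to 0 is selection after randomisation. It is decided by the same visit's VAS, which is not in the 5D model, and it removes the best outcomes.

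**Size (illustrative)**

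- n = 112 planned per arm (Protocol 5.6). The number available after termination is not given.
- p = share with VAS above zero on Day 1. The documents do not give it; I assume 10–50%.
- r = 25%, the upper pruritus rate that Protocol 4.2.2 expects at 1.5 and 2 mg, used as a stand-in for new itch among subjects without itch on Day 1.

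No 5D baseline per arm = n(1 − p). New-onset cases outside the 5D change analysis per active arm = n(1 − p)r.

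| p | With a baseline 5D | Without | New onset left out at r = 25% |
|---|---|---|---|
| 10% | 11.2 | 100.8 | 25.2 |
| 30% | 33.6 | 78.4 | 19.6 |
| 50% | 56.0 | 56.0 | 14.0 |

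The last column is the softer one. The rate r counts events over a period, not subjects itching at a given visit, and 25% is the protocol's upper expectation.

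**The case against.** **Administration may not have been conditional.** Footnote 15 speaks of every subject, and Sections 7.1.2 and 7.1.3 treat the two scales as a pair. The next footnote restricts the DLQI in so many words to subjects who reported pruritus, and footnote 15 has no such words for the 5D. If everyone completed both scales, nothing is lost. This stands as a real alternative, and the binder might settle it. It does not remove the point: footnote 15 allows fewer than two scales and refers back to 8.3.5, the one section that states a condition.

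**The SAP already scores no itch.** A reader might infer that the SAP has no 5D value for a subject without itch. That goes too far, since Appendix B names 5. What is missing is the sentence that assigns 5 when VAS = 0 and the form was not given. The missing-domain rule may be meant for partly completed forms, and the no-imputation note sits under sample code, so neither clearly forbids the derivation. Table 2 also refers to Appendix B for the VAS derivation, which is not in the text available to me, so a linking rule could be there.

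**Conflict with ITT.** A reader might infer that the restriction contradicts SAP 8.6.3. It does not. ITT says who is eligible, not who has data, and SAP 7.2.1 runs the primary ITT analysis on subjects with endpoint values only. The weakness is informative missing data.

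**New itch is seen elsewhere.** This is correct. VAS absolute change and the adverse event tables capture it. Observed 5D summaries would include it among subjects with VAS above zero at the visit, with n shown. The protocol itself (11.8) promises descriptive pruritus summaries and leaves modelling optional.

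**Conclusion.** The point holds conditionally. If Protocol 8.3.5 was applied as written, and no linking rule exists in text I could not see, subjects with VAS = 0 on Day 1 have no 5D change, no percentage change and no place in the 5D mixed model. Itch that starts on treatment in them is not counted there, and resolution to VAS = 0 in others is missing at those visits.

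The size cannot be established from the documents. The 56–101 per arm without a 5D baseline rests on the planned 112 and on an assumed 10–50% itching on Day 1.

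A reader might infer that the trial would miss drug-induced itch. The documents do not support that: the gap is confined to the 5D, and no primary or stopping decision rests on it. Termination does not remove it either. SAP Section 9 limits the later data to summary statistics after Week 12 but does not list the 5D analysis among those dropped. I rate it minor to moderate.

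**What to change.** 1. In SAP Appendix B and 8.6.3.2.1, state that at any visit, including Day 1, where VAS = 0 was recorded and the 5D was not given, each domain is derived as 1 and the total as 5. The shared two-week recall supports this: a maximum itch of zero over that period is the no-pruritus state on the 5D.
2. Keep the existing missing-domain rule where VAS is above zero and the 5D is incomplete. Leave the 5D missing where the VAS is missing too.
3. Run the 5D summaries and the mixed model on all ITT subjects with an observed or so derived 5D, and show by arm and visit how many values were derived.
4. Reconcile Protocol 8.3.5 with 7.1.2, 7.1.3 and footnote 15 on who completes the 5D, and record what sites did.
5. Minor: do not report percentage change in VAS where baseline VAS is 0, because the formula in Table 2 then divides by zero.

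The cost is one derivation rule and one clarifying sentence, using VAS data that are already scheduled. Protocol 11.1 allows SAP changes only before unblinding. If that has passed, the rule can be reported and justified as a deviation in the study report, as SAP Section 1 provides.
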